## STATISTICAL METHODS

Maximum 60 patients are planned for enrollment into this clinical trial.

Safety Analysis. All patients who receive at least one dose of the investigational treatment will be included in the safety population. All safety analyses will be performed on the safety population. Adverse Events (AE) will be coded according to the MedDRA adverse event dictionary. The results will be tabulated to examine their frequency, organ systems affected, and relationship to study treatment. The results of laboratory tests will be evaluated similarly.

Efficacy Analysis. Efficacy results, including but not limited to ORR24, BORR, DOR, DCR, TTR, PFS, and OS for patients enrolled into Part A will be provided using descriptive statistics. Objective responses will be evaluated according to both RECIST v1.1 and Response Evaluation Criteria In Solid Tumors for Immunotherapeutics (iRECIST).

Note: Confirmatory scans are required for all determinations of objective response (PR or CR), Stable disease(SD) and disease progression (PD). Confirmatory scans must be performed at least 4 weeks later.

Part B follows a Simon Two-Stage mini-max design. The sample size for the first stage of Part B is 15 patients; the sample size for the second stage is 13 patients, for a total of 28 patients. Patients from Part A without a DLT, who receive the recommended Phase 2 treatment regimen and who are considered evaluable for efficacy will be included in the analysis for Part B Stage 1. For a null hypothesis ORR24 of 0.15 and an alternative hypothesis ORR24 of 0.35, the sample size of 28 subjects will provide a one-sided significance level of 5% and a power of 80%. For Stage 1, a minimum of three patients must demonstrate a response (PR or better) to proceed to the second stage. Study has passed the first stage of Simon-Two stage design. If Stages 1 and 2 are completed, a minimum of 8 patients must demonstrate a response (PR or better) to reject the null hypothesis. If a patient's responses could not be confirmed, that patient will not be included in the primary efficacy population for ORR24.

Part C is to evaluate efficacy in larger patient population.

In Keynote-158 study (pembrolizumab monotherapy in patients who have progressed with standard of care systemic therapy), ORR in total patients (i.e. regardless of PD-L1 status) and with CPS  $\geq 1$  were 12.2% and 14.6%, respectively.

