# 22.1.2 **Tumor Imaging During the Study**

The first on-study imaging assessment should be performed approximately 9 weeks ( $\pm 3$  days]) from the date of treatment initation. Subsequent tumor imaging should be performed every 9 weeks ( $\pm 3$  days at Week 19,  $\pm 7$  days for subsequent timepoints) or more frequently if clinically indicated. Imaging timing should follow calendar days and should not be adjusted for delays

in cycle starts. Imaging should continue to be performed until disease progression is identified by the investigator (unless the investigator elects to continue treatment and follow iRECIST), the start of new anticancer treatment, withdrawal of consent, or death, whichever occurs first. All supplemental imaging must be submitted to the central imaging vendor.

Objective response and stable disease should be confirmed by a repeat imaging assessment. Tumor imaging to confirm SD, PR or CR should be performed at least 4 weeks after the first indication of a response is observed. Participants will then return to regular scheduled imaging, starting with the next scheduled imaging time point. Participants who receive additional imaging for confirmation do not need to undergo the next scheduled tumor imaging if it is less than 4 weeks later; tumor imaging may resume at the subsequent scheduled imaging time point. Note: Response does not typically need to be verified in real time by the central imaging vendor.

Per iRECIST (Appendix 6 and Section 22.3), disease progression should be confirmed by the site 4 to 8 weeks after site-assessed first radiologic evidence of PD in clinically stable participants. Participants, who have unconfirmed disease progression may continue on treatment at the discretion of the investigator until progression is confirmed by the site, provided they have met the conditions detailed in Section 22.3. Participants who receive confirmatory imaging do not need to undergo the next scheduled tumor imaging if it is less than 4 weeks later; tumor imaging may resume at the subsequent scheduled imaging time point, if clinically stable. Participants, who have confirmed disease progression by iRECIST, as assessed by the site, will discontinue study treatment. Exceptions are detailed in Section 22.3.

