- 15. Radiographic evaluations of tumor burden by RECIST v1.1 will be performed by a blinded independent central reviewer approximately every 9 weeks, or more frequently as clinically indicated, and at End of Study if the reason for discontinuation is other than for confirmed radiologic disease progression. Confirmatory scans are required approximately 4 weeks after any scan that indicates either an objective response, stable disease or disease progression.
- 16. An optional GX-188E administration may be given at week 46 if it is in the best interests of the patient, as determined by the investigator, once the patient has completed 37 weeks of treatment. Additional GX-188E administration(s) may be given to the subject after discussion with the sponsor.
- 17. The End of Study (EOS) visit must occur within 28 days of treatment discontinuation/completion (Week 103 Day 1) and prior to initiation of any new anti-cancer thepapy/regimen.

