#### APPENDIX 5: RECIST CRITERIA VERSION 1.1

Source: Eisenhauer et al., 2009

Sponsor's Note: Confirmatory scans are required approximately 4 weeks after any scan that indicates either an objective response or disease progression

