# **Evaluation of best overall response**

The best overall response is the best response recorded from the start of the study treatment until the end of treatment taking into account any requirement for confirmation. The patient's best overall response assignment will depend on the findings of both target and non-target disease, will also take into consideration the appearance of new lesions and will depend upon confirmatory scans. For this study, determinations of either CR, PR or PD require a confirmatory scan at least 4 weeks later. This is described further in Table B below.

Table B.Best Overall Response

Target Lesions	Non-Target Lesions	New Lesions	Overall Response	Best Response for this Category Also Requires
CR	CR	No	CR	≥4 weeks confirmation
CR	Non-CR/ Non-PD	No	PR	≥4 weeks confirmation
PR	Non-PD	No	PR	
SD	Non-PD	No	SD	documented at least once ≥4 weeks from baseline
PD	Any	Yes or No	PD	
Any	PD*	Yes or No	PD	no prior SD, PR or CR
Any	Any	Yes	PD	

\* In exceptional circumstances, unequivocal progression in non-target lesions may be accepted as disease progression

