#### 15. EFFICACY OUTCOMES

Tumor response to treatment will be evaluated using both RECIST v1.1 and iRECIST. For each patient with objectively measurable disease and who meet the criteria for inclusion in the Efficacy Evaluable population, response to therapy will be calculated. The analysis of ORR24, BORR and DCR per RECIST v1.1 will also be performed in safety population as sensitivity analysis.

RECIST 1.1 will be used by BICR as the primary measure for assessment of tumor response, date of disease progression, and as a basis for all protocol guidelines related to disease status (e.g., discontinuation of study treatment). All efficacy endpoints will be evaluated and categorized using RECIST 1.1. Confirmatory scans are required for all determinations of objective response [Partial response (PR) or Complete response (CR)], Stable disease (SD) and disease progression (PD). Confirmatory scans must be performed at least 4 weeks later.

Investigator assessment of tumor response based upon RECIST v1.1 will be analyzed in the same way as the corresponding BICR-assessed endpoints (except Kaplan-Meier curves which will only be presented for BICR assessment). Concordance between BICR and Investigator assessments will be summarized at a patient level for BOR.

iRECIST is based on RECIST 1.1, but adapted to account for the unique tumor response seen with immunotherapeutic drugs. iRECIST will be used by the investigator to assess tumor response and progression and make treatment decisions. When clinically stable, participants should not be discontinued until progression is confirmed by the Investigator, working with local radiology, according to the rules outlined in Appendix 6 of protocol. This allowance to continue treatment despite initial radiologic PD takes into account the observation that some participants can have a transient tumor flare in the first few months after the start of immunotherapy, and then experience subsequent disease response. This data will be captured in the clinical database.

Efficacy endpoints are as follows.

- Objective Response Rate within 24 weeks (ORR24)
- Best Overall Response Rate (BORR)
- Progression-Free Survival including 6-month PFS rate and median PFS time
- Overall Survival including 6-month OS rate and median OS time
- Disease Control Rate
- Duration of Response
- Time to Best Response

Document: \(\)\ieedc-vnac01\\Biosdata\\Genexine\\GX-188E\\GYA02599\\Biostatistics\\Documentation\\SAP\)

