#### **15.1.** PRIMARY EFFICACY ENDPOINTS

The primary efficacy variable is BICR-assessed ORR24 by RECIST 1.1 in Part B and C.

Best overall response within 24 weeks (BOR24) is the best objective response achieved within the first 24 weeks of treatment prior to study discontinuation. All available response designations will contribute to the BOR24 determination. If a patient's BOR24 could not be confirmed, that patient will not be included in the primary efficacy population for ORR24. Additional patients will be enrolled to meet the study hypothesis. Any CR or PR must be confirmed by a sequential assessment that is at least 4 weeks apart. The confirmation rule is defined in Table 2 (please refer to RECIST 1.1 [1]). The confirmed response will be determined before analysis. The number and percentage of patients in each category of best overall response CR, PR, SD, PD or Not Evaluable (NE) will be provided.

ORR24 is the proportion of efficacy evaluable patients who achieve an objective response (PR or CR) within 24 weeks prior to study discontinuation. The number and percentage of patients who achieve best overall response of PR or CR will be summarized.

If the first responses can be confirmed by the second response within 24 weeks of treatment. they will be included as responses for ORR24. Also, If the first response within 24 weeks is confirmed by the second response after 24 weeks of treatment, the first response should be included as response for ORR24.

Table 2. Best overall response when confirmation of CR and PR is required per RECIST 1.1 Guideline

Overall response  First time point	Overall response Subsequent time point	Best overall response
CR	CR	CR
CR	PR	PR, or SD provided at least 28 days' duration, otherwise PD a
CR	SD	SD provided at least 28 days' duration, otherwise PD

Document: \(\)\ieedc-vnac01\\Biosdata\\Genexine\\GX-188E\\GYA02599\\Biostatistics\\Documentation\\SAP\)

Author: [name] Version Number: 1.1

Version Date: 05Sep2022

Template No: CS TP BS016 Revision 6 Reference: CS WI BS005

Analysis Plan Page 29 of 48

CR	PD	SD provided at least 28 days' duration, otherwise PD
CR	NE	SD provided at least 28 days' duration, otherwise NE
PR	CR	PR
PR	PR	PR
PR	SD	SD
PR	PD	SD provided at least 28 days' duration, Otherwise PD
PR	NE	SD provided at least 28 days' duration, Otherwise NE
NE	NE	NE

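### The confirmatory-scan texts disagree on stable disease: the number of looks by Day 168 is left open (4, or 2 to 3), and the SAP gives two answers for a patient with a single SD scan

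*Protocol*

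**What the plan says.** Seven places give the confirmatory-scan rule, and no text ranks them for scan scheduling.

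- **Protocol Appendix 1**, second schedule, footnote 15: "Confirmatory scans are required approximately 4 weeks after any scan that indicates either an objective response, stable disease or disease progression". Footnote 17 of the first schedule uses the same words.
- **Protocol 22.1.2**: "Tumor imaging to confirm SD, PR or CR should be performed at least 4 weeks after the first indication of a response is observed". The patient then returns to the regular schedule. A skip rule follows: "Participants who receive additional imaging for confirmation do not need to undergo the next scheduled tumor imaging" when that imaging would come less than 4 weeks later.
- **Protocol Appendix 5**, sponsor's note: "Confirmatory scans are required approximately 4 weeks after any scan that indicates either an objective response or disease progression". The best-overall-response text there adds: "For this study, determinations of either CR, PR or PD require a confirmatory scan at least 4 weeks later". Neither lists SD, and Table B asks only that SD be documented once, 4 weeks or more from baseline.
- **Protocol Synopsis (Statistical Methods) and SAP 15** agree with each other. The SAP reads "Confirmatory scans are required for all determinations of objective response [Partial response (PR) or Complete response (CR)], Stable disease (SD) and disease progression (PD", with the repeat at least 4 weeks later.

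For the primary endpoint, SAP 15.1 confirms CR and PR by Table 2 and adds: "If the first response within 24 weeks is confirmed by the second response after 24 weeks of treatment, the first response should be included" as a response. It also takes a patient out of the primary efficacy population if her best response within 24 weeks (BOR24) could not be confirmed. Further on, it assigns SD to a patient whose only post-dose assessment, 28 or more days after first dose, shows CR, PR or SD.

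**The concern.** ORR24 is counted inside a fixed 24-week window and compared with a fixed 12.2%, with no concurrent control. The number of times a patient is looked at inside the window, and who is in the denominator, should both follow from one stated rule. BICR determines the endpoint but can read only the scans that sites take, so a site's choice of text sets the number of looks.

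The second issue concerns a different patient: one with a single SD scan and no repeat. One reading of the SAP drops her and another keeps her as a non-responder. If that is settled after the data are known, it can decide a close result.

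**Working it through.** **Step 1. The texts side by side**

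| Place | Is SD to be confirmed? | Trigger | Timing |
|---|---|---|---|
| Appendix 1, footnotes 15 and 17 | yes | any scan | about 4 weeks |
| Protocol 22.1.2 | yes | first indication | at least 4 weeks, no upper limit |
| Appendix 5, sponsor's note | not listed | any scan | about 4 weeks |
| Appendix 5, best overall response | not listed | each determination | at least 4 weeks |
| Synopsis; SAP 15 | yes | all determinations | at least 4 weeks |

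Three points conflict: SD in or out, the trigger, and the timing. No row omits CR or PR.

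**Step 2. The calendar** (Protocol 22.1.2 and Appendix 1). Scheduled scans fall at:

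- Week 10 Day 1 = 9 × 7 + 1 = Day 64
- Week 19 Day 1 = 18 × 7 + 1 = Day 127
- Week 28 Day 1 = 27 × 7 + 1 = Day 190, or Day 183 at the earliest with its 7-day window

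The endpoint window closes at 24 × 7 = Day 168, so Week 19 is the last scheduled look inside it.

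**Step 3. Scans by Day 168 in continuing SD.** The documents give no count to reproduce.

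- Appendix 1, each scheduled scan confirmed at +28 days: Days 64, 92, 127, 155 = **4**. With the 3-day windows the fourth falls on Days 152 to 158, still inside.
- Protocol 22.1.2, first SD confirmed at +28 days: Days 64, 92, 127 = **3**.
- Protocol 22.1.2, the Week 19 scan itself serving as confirmation (127 − 64 = 63 days, which is at least 28): **2**.
- Protocol 22.1.2, confirmation on day d with 127 − d < 28, that is Days 100 to 126, and Week 19 skipped: **2**. With d = 100, the next scheduled scan is 190 − 100 = 90 days later, leaving the last 168 − 100 = 68 days of the window without one.
- Appendix 5, no SD confirmation: Days 64, 127 = **2**.

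**Step 4. Link to ORR24.** A PR that first becomes visible between Days 127 and 155 is seen at Day 155 under the four-scan reading. It counts even if confirmed after Day 168. Under the other readings it is first seen at about Day 190 and does not count. A skipped Week 19 scan can likewise miss a response.

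**Step 5. The denominator.** The success rule (Protocol 24.3) is a Clopper-Pearson lower 95% limit above 12.2%. The planned size reproduces: n = 45 needs 11 responders, has power 0.974 at 37%, and 45 / 0.75 = 60. The lower limit for x responders of n is the 2.5% point of a Beta(x, n − x + 1) distribution.

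| x/n | Lower limit | Above 12.2%? |
|---|---|---|
| 14/60 | 13.38% | yes |
| 13/60 | 12.07% | no |
| 13/59 | 12.29% | yes |
| 10/45 | 11.2% | no |
| 10/42 | 12.05% | no |
| 10/41 | 12.36% | yes |

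At 60 evaluable patients (Protocol 24.8), one exclusion at the boundary reverses the result. At 45 it takes four. These are results under the interval rule. The plan also names a two-sided exact test without saying how the second tail is formed. Doubling the upper tail gives 2 × 0.0270 = 0.054 for 13/60, which agrees with the interval. The convention of summing all outcomes no more likely than the one observed would already reject at 13/60.

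**The case against.** The case for calling this a minor drafting matter is substantial, and most of its facts stand.

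- *Confirmation of response is settled.* SAP Table 2 governs it and every text requires it. This stands. A reader might infer that the definition of a response is itself unclear; the documents do not support that.
- *There are not seven incompatible rules.* Several places match. A site that scanned about 4 weeks, and not under 28 days, after every scheduled scan would meet nearly all of them. This stands, but a site doing less can also point to a text that allows it.
- *The skip-rule gap is a corner case.* It needs a late confirmation, on Days 100 to 126. A 4-week confirmation does not trigger it even at the window limits: first scan Day 67, confirmation Day 95, Week 19 scan Day 124, a gap of 29 days. This stands.
- *The boundary case is remote.* The chance of exactly 13 responders of 60 is 0.015 at a true rate of 12.2% and 0.005 at 37%. It also assumes no replacement, whereas SAP 15.1 foresees enrolling additional patients. Both points stand and limit the size.
- *The single-assessment rule already answers the denominator question.* Only in part. It assigns a category but does not say that SD so assigned counts as confirmed, and the exclusion sentence in the same section is not limited to CR and PR.
- *Scans taken as clinically indicated vary the number of looks anyway.* True. One rule fixes required scans only.

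**Conclusion.** The conflict is in the current text and should be removed. For continuing SD it leaves the required scans by Day 168 at 4 if each scheduled scan is confirmed under Appendix 1, and otherwise at 2 to 3. Separately, the SAP both excludes and retains a patient with one unrepeated SD scan. With 60 evaluable patients, 13 responders and no replacement, one such exclusion moves the lower limit from 12.07% to 12.29% and turns failure into success.

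A reader might infer that extra looks inflate ORR24 or raise the false-positive rate. The documents do not support this. They do not say which text sites followed or how often responses first appear between scans. A PR seen at Day 155 and later confirmed is a genuine response. The routes also run both ways: an added look can find a response, a skipped Week 19 scan can miss one, and a repeat scan that confirms SD keeps a non-responder in the denominator. Neither the size nor the direction of any net effect is shown.

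**What to change.** 1. **SAP 15.1:** state that a patient whose only scan, 28 or more days after first dose, shows SD stays in the ORR24 denominator as a non-responder. The repeat scan remains a scheduling instruction; this sentence covers the patient who does not get it.
2. **Scan wording:** align all seven places on the 22.1.2 approach, with one confirmatory scan at least 4 weeks after the first indication and then a return to the 9-weekly schedule. State that the Week 19 scan is not waived by a confirmatory scan, and that a PR or CR first seen later still gets its own confirmation. Leave the 22.1.2 rule for progression as it is.
3. **Reporting:** tabulate evaluable scans by Day 168 for each patient.

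The cost is a protocol amendment needing IRB/IEC and sponsor approval (Protocol 25.4) across at least 8 sites (Protocol 10.6), one SAP sentence and one table. Patients with unchanged SD are spared repeat imaging, and a few keep a Week 19 scan they could otherwise have skipped. The change cannot alter scans already taken, and Stage 1 of Part B has passed, so the pooled data will contain more than one schedule. The table shows how far that matters.

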### **Schematic Flow Chart**

# APPENDIX 2: LIST OF LIVE VACCINES.

Source: https://www.cdc.gov/vaccines/pubs/pinkbook/downloads/appendices/B/usvaccines.pdf

Patients who received any of the live vaccines listed below within 30 days of Screening are excluded from the study and cannot be enrolled.

Vaccine	Trade Name	Manufacturer	Type / Route
Adenovirus	Adenovirus Type 4 & Type 7	Barr Labs Inc.	Live Viral / Oral (tablets)
Herpes Zoster (Shingles)	Zostavax	Merck	Live Attenuated Viral / SC
Influenza	FluMist ®	Medimmune	Live Attenuated Viral / Intranasal (spray)
Measles, Mumps, Rubella	M-M-R ® II	Merck	Live Attenuated Viral / SC
Measles, Mumps, Rubella, Varicella	ProQuad ®	Merck	Live Attenuated Viral / SC
Rotavirus	RotaTeq®	Merck	Live Viral / Oral (liquid)
	Rotarix®	GlaxoSmithKline	Live Viral / Oral (liquid)
Typhoid	Vivotif®	PaxVax	Live Attenuated Bacterial / Oral (capsules)
Varicella	Varivax ®	Merck	Live Attenuated Viral / SC
Varicella	Suduvax®	Green Cross	Live Attenuated Viral / SC
Vaccinia (Smallpox)	ACAM2000®	sanofi	Live Attenuated Viral / Percutaneous
Yellow Fever	YF-Vax ®	sanofi	Live Attenuated Viral / SC
BCG for Tuberculosis		[multiple manufacturers]	Live attenuated / SC

# APPENDIX 3: MOORE'S CRITERIA FOR DETERMINING PROGNOSIS IN CERVICAL CANCER

Source: Moore DH et al., 2010

All study participants should be categorized as low-risk, mid-risk or high-risk based upon the criteria and instructions below.

	Risk Factor		
Criterion	1 point each	0 points each	
Race	Black	Non-Black	
GOG Performance Status*	1 or 2	0	
Site of Disease	Pelvis	Non-pelvis	
Prior Platinum Agent as a Radiosensitizer?	Yes	No	
1st Recurrence within 1 year since diagnosis?	Yes	No	

Add number of risk factors, or points, to obtain the Total Risk Score

Total Score	Risk Category
0-1	Low-Risk
2-3	Mid-Risk
4-5	High-Risk

# \*GOG Performace Status

GOG Score	Activity Level
0	Fully active, unrestricted activities of daily living
1	Ambulatory, but restricted in strenuous activity
2	Ambulatory, and capable of self care. Unable to work. Out of bed for greater
	than 50% of waking hours
3	Limited self care, or confined to bed or chair 50% of waking hours. Needs
	special assistance
4	Completely disabled, and no self care
5	Dead

## APPENDIX 4. CLINICAL LABORATORY TESTS

CLINICAL LABORATORY TESTS RESULTS WITHIN 4 WEEKS (8 WEEKS FOR SEROLOGY) PRIOR TO THE START OF STUDY TREATMENT WILL BE CONSIDERED AS ELIGIBLE TEST RESULTS FOR SCREENING PROCEDURES.

## **Hematology (Peripheral Blood Sample)**

- Hemoglobin and hematocrit
- RBC count
- White blood cell count with differential
- Platelet count

